Correlation of Spinopelvic Movement with
Lateral Radiographs to Assess Spine Motion
Prior to Total Hip Arthroplasty.

NCT05117229

6/21/2021

6-21-2021

Correlation of Spinopelvic Movement with Lateral Radiographs to Assess Spine Motion Prior to Total Hip Arthroplasty.

Design: Prospective pilot study

Aims:

- 1) To evaluate the correlation between a novel pelvic MetaWear sensor that assesses spinopelvic motion with lateral sit-to-stand radiographs.
- 2) To evaluate the relationship between a novel pelvic sensor with pelvic tilt, sacral slope, and lumbar lordosis.

Background: Spinopelvic relationships are increasingly recognized as an important part of total hip arthroplasty and determinant of stability after THA. A number of recent papers in the literature have correlated stiffness of the spinopelvic parameters and the potential risk of total hip arthroplasty dislocation. Most commonly, assessment is performed with lateral sit-to-stand radiographs where changes of less than 10 degrees in sacral slope have been described as stiff spines and could represent patients at increased risk of instability. Given the dynamic nature of the hip/spine biomechanics, which is further influenced by relative stiffness of the hip/spine complex, it remains to be determined how the patient's actual motion impacts these radiographic parameters. MetaWear sensors positioned on the pelvis can potentially provide meaningful spinopelvic motion parameters and could eliminate the need for additional radiation needed to obtain lateral radiographs. The correlation between the MetaWear sensor obtained spinopelvic motion and radiographic data obtained from the more traditional lateral sit to stand radiographs is needed.

We will prospectively evaluate 40 patients presenting for surgery at the Division of Hip and Knee Arthroplasty at Mayo Clinic. An assessment of pelvic motion will be obtained through MetaWear sensors. Data capture will then be verified by the Research Coordinator. Preliminary data shows in 2019, OrthAlign, Inc. conducted an internal study utilizing one sensor device strapped to the femur and one sensor device attached to the skin by the patient's sacrum using the same devices and adhesive in the proposed study. The study included 10 employees with no prior knowledge of everyone pelvic or spinal mobility. A physical therapist conducted the study according to the protocol consistently across all individuals. Measurements were taken while sitting, standing, and leaning forward. All intended data was able to be collected with no adverse events. Across the patient population, the average change in pelvic mobility between sitting and standing was 11.86° with a standard deviation of 6.99° , minimum of -1.07° and a maximum of 28.25° . In a study using radiographs, Seyler et al.¹ found an average of 19.2° , standard deviation of 9.9° , min of 1.6° , maximum of 37.5° in change in pelvic tilt across 24 subjects. Nine total measurements were taken per individual. Three sets of measurements were taken. Each set contained three measurements under the same conditions. Between datasets, the sensors were removed and

re-applied. The standard deviation within and across datasets were calculated for each patient. The standard deviation within datasets was just under 3.0° and the standard deviation across datasets was 3.2° . These standard deviations were compared to radiographs study data². The study showed standard deviations between approximated 2.7° and 3.5° for radiograph measurements of sacral slope and APP angle during standing and sitting positions. Therefore, we concluded our study produce feasible pelvic range of motion results between sitting and standing positions with repeatability and reproducibility comparable to radiograph technology.

Methods: Data from the MetaWear sensors will be collected directly into the sensor and downloaded onto a secure Excel sheet after transfer to specialized app on an IPAD. These patients will have a lateral sitting and standing lumbar radiographs which will take approximately 15 minutes. All patients will have a modern and innovative MetaWear sensor placed on their pelvis which should take an additional 15 minutes to place on the research subjects (Figure 1: showing location of the MetaWear sensor placement). The patients will then obtain the appropriate radiographs with the sensors in place and appropriate correlations between sensor data and radiographs will be made. Radiographs being taken include lateral sitting, standing, and pelvis images.

Included Patients: Age 18+

Ability to provide informed consent

40 total

Sex: men & women

Hip pathology: 40 subjects presenting for total hip arthroplasty or joint preservation procedures

Age: 20 patients greater than 70 years, 10 patients between 50-70, and 10 patients 18-50

Pregnancy test: Women in childbearing ages between 18 and 50 will be required to perform a urine pregnancy test prior to inclusion

Excluded patients: Exclude patients with lumbosacral hardware, contralateral THA, or DJD in the contralateral hip, pregnant women, those who have an allergy to glue or adhesives, or those unwilling to be tested.

Withdraw Criteria: If a patient is unable to complete the required imaging due to inability to sit or stand during radiographs, the patient may withdraw from the research study. Poor radiograph images that do not provide appropriate measurements; additionally, if the MetaWear sensor is unable to track patient movement.

Enrollment process: Patients will be deemed potentially eligible by surgical teams in the Division of Hip and Knee Reconstruction and will be approached by a study coordinator from the Department of Orthopedic Surgery. The study coordinator will obtain a master list of

enrolled patients, managed in Ptrax and will determine if the patient demographics constitute an unfilled spot on the list. If this is the case the study coordinator will discuss the study in detail with the patient and if they agree to participate, we will obtain written informed consent. Subjects will receive \$25.00 for their participation. Radiographs for the study that are not part of the standard of care and will be covered by the study and not charged to the patient or their insurance.

The main risk of the study is incremental radiation exposure from 2 research related radiographs. An additional risk includes reaction to adhesive tape. No other risks were identified. The adhesive tape is a FLEXcon® dermaFLEX™ which meets ISO 10993 standards for direct skin contact. The contained H-566 adhesive is non-cytotoxic, non-irritating and non-sensitizing, as defined by the ISO-10993 standard

The benefit of the study is to improve the future patient care and add to the body of scientific knowledge in this important area. Radiographs: Lateral lumbar radiographs that are not the standard of care for hip surgery patients at this time and will be obtained for research purposes. This is a lateral standing and lateral sitting radiograph as part of the research and will be covered by the study.

Post-radiographic evaluation: Following attainment of all radiographs the investigative team will perform measurements on all radiographs including PI, PT, SS, LL. Interobserver reliability statistics will be determined. Any discrepancies between reviewers of more than 2 degrees will be resolved by a third reviewer.

Assessment of pelvic motion will be obtained through the MetaWear sensors. Preliminary data shows (Add the prelim data obtained for health subjects here) Data from the MetaWear sensors will be collected directly into the sensor and downloaded onto a secure Excel sheet.

There will be no post-radiographic study follow-up for the patients. If a gross abnormality is identified on research-related radiographs the patient will be notified by the surgical team.

Statistical analysis: No power analysis was performed as this is a pilot study to determine the correlations between PI, PT, SS, LL and patient sensor obtained motion. Statistical analyses will be performed by Mayo Stats (Budget 2K more or less plus 40% indirect)

The total of 40 subjects was chosen to allow balance of age, sex, and hip disease status as these parameters may influence measurements.

Following collection and annotation of all data, a password protected spreadsheet on a departmental-secured server will be shared with a statistician from the Division of Biomedical Statistics and Informatics. Categorical data will be tabulated as counts and percentages and continuous data as means and ranges with standard deviations and confidence intervals as appropriate. Correlations and means between radiographic parameters obtained from lateral radiographs will be calculated and correlated with spinopelvic motion obtained through the MetaWear sensors. Sensitivity analysis or adjusted analyses will be performed for age, sex, and hip pathology as deemed appropriate by the statistician.

Device Description:

Each device is a MetaWear, MotionC wearable sensor. The device contains a circuit board with a MEMS gyroscope, accelerometer, magnetometer, barometric pressure, and light ambient sensor. Not all sensors are used for this study. The circuit is encased in a plastic housing. Real-time communication to a tablet is achieved via BluetoothLE wireless communication. The device is FCC, CE, IC and RoHS compliant.

Adverse Events:

Adverse events will be monitored and reported to the PI who will make the data available to the DSMB. However, we do not anticipate any adverse event occurring with the use of such sensor technology. The only adverse even would be associated with sensitivity to adhesive tape during the MetaWear sensor placement.

References:

¹ Sutter EG, Wellman SS, Bolognesi MP, Seyler TM. “A Geometric Model to Determine Patient-Specific Cup Anteversion Based on Pelvic Motion in Total Hip Arthroplasty.” *Adv Orthop.* 2019 May 2;2019:4780280. doi: 10.1155/2019/4780280. PMID: 31186967; PMCID: PMC6521545.

² J.-Y. Lazennec, M.-A. Rousseau, A. Rangel, M. Gorin, C. Belicourt, A. Brusson, Y. Catonné

“Pelvis and total hip arthroplasty acetabular component orientations in sitting and standing positions: Measurements reproducibility with EOS imaging system versus conventional radiographies”

Revue de Chirurgie Orthopédique et Traumatologique, Volume 97, Issue 4, June 2011, Pages 375-383

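### Is a 2° trigger for third-reader resolution too tight, given the radiographic SD of 2.7–3.5° that the protocol cites?

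*Protocol*

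**What the plan says.** The protocol's Post-radiographic evaluation paragraph has the team "perform measurements on all radiographs including PI, PT, SS, LL". It continues: "Interobserver reliability statistics will be determined". The adjudication rule comes after that: "Any discrepancies between reviewers of more than 2 degrees will be resolved by a third reviewer". The protocol gives no basis for the 2° limit and no expected adjudication rate. It does not say how the third reading is combined with the first two.

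The Background section, in its account of the preliminary sensor data, cites a published radiographic study with "standard deviations between approximated 2.7° and 3.5° for radiograph measurements of sacral slope and APP angle". It sets these beside the sensor's own figures ("The standard deviation within datasets was just under 3.0° and the standard deviation across datasets was 3.2" degrees) and concludes that the sensor works "with repeatability and reproducibility comparable to radiograph technology".

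Under Statistical analysis the sample size is not derived: "No power analysis was performed as this is a pilot study".

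**The concern.** Adjudication rules usually aim to catch reading mistakes, so their limit sits beyond ordinary measurement error. Here the limit is 2/3.5 = 0.57 to 2/2.7 = 0.74 of one cited SD. Two competent readers with that much error would often differ by more than 2° without either having made a mistake.

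Two things would then be at stake. The radiograph is the comparator for both aims. If a single third reading replaced the pair, or selected one of the two, the reference value would be noisier than the plain mean of two readings, and the sensor–radiograph correlation would be lowered for reasons unrelated to the sensor. And if interobserver reliability were computed after resolution, it would describe the adjudication and not the readers.

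**Working it through.** **Inputs.** Trigger 2° (Post-radiographic evaluation). Radiographic SD 2.7° to 3.5°, SD of sit-to-stand change in pelvic tilt 9.9°, and 40 patients (Background). The protocol states no adjudication rate, so there is no figure of its own to reproduce.

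**Step 1: how often the rule fires.** Let each reader have independent, unbiased normal error with SD s. The difference has SD s√2, and

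p = 2[1 − Φ(2/(s√2))].

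| Reading of the SD | Value | p |
|---|---|---|
| Cited SD is one reader's error | 2.7° | 60.0% |
| Cited SD is one reader's error | 3.5° | 68.6% |
| Cited SD is already that of a difference, p = 2[1 − Φ(2/s)] | 2.7° | 45.9% |
| Cited SD is already that of a difference | 3.5° | 56.8% |
| Assumed smaller reader-only SD | 2.0° | 48.0% |
| Assumed smaller reader-only SD | 1.5° | 34.6% |
| Assumed smaller reader-only SD | 1.0° | 15.7% |

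The rate passes one half at a reader SD of 2/(0.6745 × √2) ≈ 2.10°. A majority is therefore adjudicated only if reader error makes up at least (2.10/2.7)² ≈ 60% of the cited variance at the low end, or (2.10/3.5)² ≈ 36% at the high end.

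**Step 2: what resolution does to the reference value.** Assume that the mean of two is used when the rule does not fire. The mean of two readings is independent of their difference, so two of the error variances have a closed form. The other two come from simulation under the same model. All are in units of s², for s = 2.7° and 3.5°.

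| Meaning of resolution | Error variance |
|---|---|
| No adjudication, mean of two | 0.50 |
| Third reading replaces the pair: 0.5(1 + p) | 0.80 to 0.84 |
| Third reader picks the closer reading (simulated) | about 0.66 |
| Median of three (simulated) | 0.47 to 0.48 |
| Mean of three: 0.5 − p/6 | 0.39 to 0.40 |

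Two of the four adjudication options worsen the reference and two improve it.

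**Step 3: effect on the correlation in the worst case examined.** Take 9.9° as the observed SD of a sit–stand change based on single readings. The true variance is 9.9² − 2s², and the error variance of a change is 2ks², with k from step 2. The attenuation factor is √[true/(true + error)].

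- s = 2.7°: true variance 98.01 − 14.58 = 83.43. Mean of two: √(83.43/90.72) = 0.959. Third replaces (k = 0.80): √(83.43/95.09) = 0.937.
- s = 3.5°: true variance 98.01 − 24.50 = 73.51. Mean of two: √(73.51/85.76) = 0.926. Third replaces (k = 0.84): √(73.51/94.09) = 0.884.

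For a true r of 0.8 the loss is 0.8 × 0.022 ≈ 0.02 or 0.8 × 0.042 ≈ 0.03. With n = 40, Fisher's transformation gives a 95% interval of tanh(1.0986 ± 1.96/√37), about 0.65 to 0.89.

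**Step 4: the looser alternative.** A limit at 95% of chance differences would be 1.96 × √2 × s, that is 7.5° at s = 2.7° and 9.7° at s = 3.5°. The Background describes a sacral slope change below 10° as a stiff spine.

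**The case for a change.** The best case for a change is that the protocol itself fixes the 2° limit and itself cites an SD that does not fit it, so this is more than silence left to an SAP. Much of that stands. Even at an assumed reader SD of 1.5°, about 35% of readings would be adjudicated, and a 5% rate would need a reader SD of 2/(1.96 × √2) ≈ 0.72°, roughly a quarter of the lowest SD cited. If the third reading replaced the pair, the error SD of a sit–stand change would rise from 2.7° to √(2 × 0.80) × 2.7 ≈ 3.4°, or from 3.5° to about 4.5°. That is not trivial beside a 10° stiffness limit. The remedy would also cost only wording.

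The rest is conditional. The protocol does not say whether the cited SD is between readers, within a reader, across repeat films or of a difference. The rule compares two readers, in the natural reading on the same film, so any repositioning variance in that SD drops out of their difference. The SD is given for sacral slope and APP angle. APP angle is not among the adjudicated parameters, and pelvic incidence, pelvic tilt and lumbar lordosis have no cited SD. A per-film rate across four angles cannot be derived from it, all the more because angles read from shared landmarks are unlikely to have independent errors.

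The reliability worry has no support in the text. Interobserver statistics are mentioned before resolution, and nothing says that they use adjudicated values. The ordinary meaning of interobserver reliability is agreement between the readers' own readings.

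**Conclusion.** The observation is correct: the trigger is smaller than the radiographic SD the protocol cites. On the reading that this SD is independent per-reader error, 60% to 69% of sacral slope readings would go to a third reader by chance. The rate is 46% to 57% if it is the SD of a difference, and lower if part of it is repeat-film variance.

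No change follows, for three reasons. First, the direction of any harm is undetermined: the rule adds noise if the third reading replaces or selects, and removes it if three readings are averaged or their median is taken. How to combine them, and which readings enter the reliability statistic, is operational detail that analysts fill sensibly in a reading manual or SAP. Second, the worst case examined costs about 0.02 to 0.03 on a true r of 0.8, small beside an interval of about 0.65 to 0.89 in a 40-patient pilot. This assumes that the 9.9° SD applies to these patients and that reader errors are normal and independent. Third, a strict trigger is a defensible quality rule whose certain cost is reader time. A limit of 7.5° to 9.7° would rest on the same uncertain SD and would let readers differ, without review, by nearly as much as the 10° stiffness limit. That is a trade-off on which reasonable statisticians would differ.

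### Does the statistical section correlate fixed-position angles with sensor motion, and so fail to answer Aim 1?

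*Protocol*

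**What the plan says.** Aim 1 is to correlate a sensor that "assesses spinopelvic motion with lateral sit-to-stand radiographs". Aim 2 is "To evaluate the relationship between a novel pelvic sensor with pelvic tilt, sacral slope, and lumbar lordosis", which lists angles without mentioning change. The Background describes how such films are read: "changes of less than 10 degrees in sacral slope have been described as stiff spines". The preliminary data set a sensor change beside a radiographic one. For the sensor, "the average change in pelvic mobility between sitting and standing was 11.86° with a standard deviation of 6.99" degrees; for the cited radiographic study, an SD of 9.9° "in change in pelvic tilt across 24 subjects".

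The Methods provide for sitting and standing lateral films, taken while the sensor is worn, and leave the choice of suitable correlations open. Under Post-radiographic evaluation, "the investigative team will perform measurements on all radiographs including PI, PT, SS, LL".

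The Statistical analysis section mentions the variables twice. One mention explains why no power calculation was done: "this is a pilot study to determine the correlations between PI, PT, SS, LL and patient sensor obtained motion". The other says that "radiographic parameters obtained from lateral radiographs will be calculated and correlated with spinopelvic motion obtained through the MetaWear sensors". That second sentence opens by promising correlations and means among the radiographic parameters, so its grammar is muddled and it is not a clean list of raw angles.

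**The concern.** PT, SS and LL are measured separately on the sitting and the standing film. If one of those angles is correlated with the sensor's sitting-to-standing motion, a position is set against a motion. Such a correlation depends on which film is used and on how widely patients differ in each position, as well as on sensor accuracy. A good sensor could look poor, and the sign could reverse between films. PI adds to the impression that the list was not drawn from Aim 1, since neither aim names it. The sensor is put forward as a possible replacement for films, so a misleadingly weak or strong correlation would matter. An analyst could also choose the film after seeing the results.

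**Working it through.** The plan gives no figure to reproduce: it states no power, alpha or target correlation. The check asks how much the pairing could matter, and then what the protocol actually commits to.

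**Inputs from the protocol (preliminary data).** SD of change *d*: 9.9° (cited radiographic pelvic tilt) or 6.99° (sensor, 10 employees). Film error SD *e*: 2.7° to 3.5° per film. Sensor SD: 3.0° within and 3.2° across datasets. N = 40.

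**Assumed, because the protocol gives none.** SD of the standing angle *st* and of the sitting angle *si*.

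**Formulas**, for an error-free sensor and change = sitting minus standing:
- change with change: d / √(d² + 2e²)
- sitting film: (si² + d² − st²) / (2d√(si² + e²))
- standing film: (si² − st² − d²) / (2d√(st² + e²))

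**Change with change**
- d = 9.9: 9.9/√(98.01 + 14.58) = 0.93; with e = 3.5, 9.9/√(98.01 + 24.50) = 0.89.
- If 9.9° already contains film error, √(1 − 2e²/d²) gives 0.92 and 0.87.
- d = 6.99 taken as the true SD: 0.88 and 0.82.
- But 6.99° is an observed sensor SD. Removing 3.0° to 3.2° of sensor error leaves √(48.86 − 9.00) = 6.31 to √(48.86 − 10.24) = 6.21. Then r = 6.31/√(39.86 + 14.58) = 0.86 down to 6.21/√(38.62 + 24.50) = 0.78.

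**Single-position angle**

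| Assumed st / si | d | Standing film | Sitting film |
|---|---|---|---|
| 8 / 8 | 9.9 | −0.57 to −0.59 | 0.57 to 0.59 |
| 10 / 10 | 9.9 | −0.47 to −0.48 | 0.47 to 0.48 |
| 15 / 15 | 9.9 | −0.32 | 0.32 |
| 10 / 14 | 9.9 | −0.01 | 0.68 to 0.69 |
| 8 / 8 | 6.99 | −0.40 to −0.41 | 0.40 to 0.41 |
| 8 / 14 | 6.99 | 0.68 to 0.70 | 0.90 to 0.91 |

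Within one assumed population the choice of film can change the size (10/14) or the sign (equal SDs). In the last row the sitting film exceeds change with change, so the gap can also reverse. The extremes, about −0.6 and 0.9, belong to different assumed populations. The implied sitting–standing correlation is (64 + 64 − 98.01)/(2 × 64) = 0.23 for 8/8 at 9.9°, and (64 + 196 − 48.86)/(2 × 8 × 14) = 0.94 for 8/14 at 6.99°. The second is close to a boundary, because with SDs of 8 and 14 the change SD cannot fall below 14 − 8 = 6. The two extremes should not be read as one range for one sensor.

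**Against sampling error at N = 40** (Fisher 95% intervals): r = 0.48 has 0.20 to 0.69 and r = 0.89 has 0.80 to 0.94, which separate. r = 0.75 has 0.57 to 0.86 and r = 0.82 has 0.68 to 0.90, which overlap.

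**What the protocol commits to.** No sentence selects a single-position angle for Aim 1, and none writes out the difference. Everything that describes the purpose is in terms of change: the sit-to-stand comparison in Aim 1, the sacral slope criterion in the Background, and change beside change in the preliminary data. Both films and the matching sensor record exist for each patient who completes the imaging, so the difference is a subtraction at analysis. The four-angle list is close to Aim 2, which does name angles.

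**The case for a change.** The strongest case for a change is that the protocol is not silent. It names its variables, and names them in a form that does not match Aim 1. Someone following the text could pair sensor motion with the sitting film, the standing film or the difference, and claim adherence in each case. Correlation is the only stated measure for Aim 1, and the remedy would be a sentence or two using films already planned.

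Part of this stands. The sentence is loose, and the algebra shows that a single-position pairing would be a poor test of Aim 1. But the sentence quoted most directly is a clause explaining the absence of a power calculation, and the second is too muddled to be read as a rule for raw angles. Defining a derived variable is ordinary SAP work, and a SAP may exist that is not at hand. Selective choice of film is conceivable, but this is a pilot with no stated success threshold, and a single-position result offered as the answer to Aim 1 would plainly not fit that aim. Naming PI in the list is harmless: it adds a descriptive correlation and displaces nothing.

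**Conclusion.** The observation is correct as far as it goes: the statistical text does not say whether sitting angles, standing angles or their difference enter the correlation. It is a gap that an analyst fills sensibly from the rest of the protocol, by using the sitting-to-standing change for Aim 1 and treating single-position angles and PI as descriptive, which Aim 2 permits. No data are lost under the present wording, because the change can be computed from what is collected. How much a wrong pairing would cost cannot be derived from the documents. The contrast of about 0.9 with roughly 0.3 to 0.6 holds at a change SD of 9.9° with equal position SDs of 8° to 15°, and it shrinks, vanishes or reverses under other assumptions. This conclusion rests on change being the intended variable, which the Aims, the Background and the preliminary data support and nothing excludes. No change to the plan is called for.

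### Does a sample size of 40, justified by balance on age, sex and hip disease, fail because only age has printed quotas?

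*Protocol*

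**What the plan says.** The Statistical analysis section of the protocol discloses that there is no power calculation: "No power analysis was performed as this is a pilot study to determine the correlations between PI, PT, SS, LL and patient sensor obtained motion". It then gives its one reason for the size: "The total of 40 subjects was chosen to allow balance of age, sex, and hip disease status as these parameters may influence measurements".

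The enrolment numbers are under Included Patients. Age has quotas: "Age: 20 patients greater than 70 years, 10 patients between 50-70, and 10 patients 18-50". Sex is listed as open to men and women, with no number. Hip pathology is a single line: "Hip pathology: 40 subjects presenting for total hip arthroplasty or joint preservation procedures".

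Under Enrollment process, the study coordinator consults a master list and "will determine if the patient demographics constitute an unfilled spot on the list". The contents of that list are not printed.

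The end of the Statistical analysis section covers the use of the three factors: "Sensitivity analysis or adjusted analyses will be performed for age, sex, and hip pathology as deemed appropriate by the statistician".

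**The concern.** A sample size that rests on neither power nor precision should at least match the reason given for it. Here the reason is balance on three factors, and the printed numbers do not deliver it:

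- **Age** is fixed at 2:1:1, which is not equal, and a 50-year-old fits both the 18-50 and the 50-70 band.
- **Sex** has no target.
- **Hip disease status** has no split. If it means diseased versus not diseased, it cannot vary at all, since everyone enrolled presents for surgery. If it means arthroplasty versus joint preservation, the two are pooled.

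Quotas act at enrolment, so a later analysis plan could not restore a split that was never secured. The protocol itself says these factors may influence the measurements and foresees adjusting for them. At stake is how much the adjusted analyses could show. With sex left to chance, a 10-patient age band can easily come out lopsided.

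**Working it through.** **Reproducing the total.** The age quotas give 20 + 10 + 10 = 40, which agrees with the stated size. There is no alpha, power, effect size or precision target, so no sample-size formula can be checked.

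**How uneven sex could become.** The protocol gives no sex ratio. Assume that each patient is female with probability 0.5, or 0.6 as the other end of a range, with no sex quota. Two-sided exact binomial probabilities:

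| Split | 50:50 | 60:40 |
|---|---|---|
| 7:3 or worse in a band of 10 | 34% | 44% |
| 8:2 or worse in a band of 10 | 11% | 18% |
| 25:15 or worse in all 40 | 15% | 44% |

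These look large, but a probability of imbalance is not yet a loss of information.

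**What the imbalance costs over all 40.** The standard error of an unadjusted sex contrast is proportional to √(1/a + 1/b). At 25:15 against 20:20 the ratio is √[(1/25 + 1/15)/(2/20)] = 1.033, a 3% increase.

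**What it costs after adjusting for age band.** The information on sex is the sum over bands of (women × men)/(band size). With perfect balance this is 10·10/20 + 5·5/10 + 5·5/10 = 10. For any other split, the standard error rises by the factor √(10/information). Examples:

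- Bands at 10:10, 5:5 and 8:2: information 5 + 2.5 + 1.6 = 9.1, factor 1.048.
- Bands at 14:6, 7:3 and 7:3: information 4.2 + 2.1 + 2.1 = 8.4, factor 1.091.

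Averaged over all chance splits of 20/10/10, the factor is about 1.04 at 50:50 and 1.06 at 60:40. The chance that it exceeds 1.25 is 0.1% and 1.0% respectively. A 25% inflation does arise at 8:2 inside one band of 10, since √[(1/8 + 1/2)/(2/5)] = 1.25. But that is a sex contrast within a single age band, which the protocol does not plan.

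**What it costs the aims.** The aims are correlations between the sensor and the radiographs. By Fisher's z, the width of the interval for a given correlation depends on the number of patients, not on the sex split. For an assumed r of 0.5 and n = 40, the 95% interval is tanh(0.549 ± 1.96/√37), or 0.22 to 0.70, whatever the mix of men and women.

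**Does 40 allow balance?** Take hip disease status as the two procedure types (an assumption). Equal cells in a band of 10 would need 10/4 = 2.5 patients each, which is impossible. Balance on each factor's margin is possible:

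- Order the cells as men/arthroplasty, men/preservation, women/arthroplasty, women/preservation.
- Cells of 3, 2, 2, 3 in one band of 10 give 5:5 on sex and 5:5 on procedure.
- Cells of 2, 3, 3, 2 in the other band do the same, and the two bands together hold 5 in every cell.
- The band of 20 takes 5 per cell.

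So 40 does allow sex and procedure to be balanced within every age band.

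**What sex quotas would cost.** The expected number of patients needed to fill k men and k women at 50:50 is 2k[1 + C(2k,k)/2^(2k)]. This is 12.46 for 5/5 and 23.52 for 10/10, so 2 × 12.46 + 23.52 = 48.4 in total. At 60:40 the sums are 13.48 and 25.89, so 52.8 in total. About 8 to 13 eligible, willing patients would be turned away.

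**The case for a change.** The strongest reply is that if balance is merely possible, then 40 has no stated basis, since a size that permits balance also permits imbalance. The coordinator's list is described as a list of enrolled patients. Reading sex quotas into the word demographics is an inference, and hip pathology is not a demographic at all.

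Much of this stands. The rationale is thin, and whether the list holds sex slots cannot be told from the protocol. Hip pathology is the weakest of the three factors. If joint preservation makes up an assumed 5%, 10% or 20% of patients, the chance of four or fewer such patients among 40 is 95%, 63% or 8%. Adjustment for it could then rest on a handful of people.

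None of this leads to a better plan. The protocol openly calls itself a pilot without a power calculation, so rewording the rationale would change neither the size nor any result. Declaring that pathology will only be described would conflict with the adjustment for it that the Statistical analysis section foresees. That section leaves adjustment to the statistician's judgement, so a factor with too few patients on one side can be handled when the counts are known.

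**Conclusion.** The facts are as stated: the reason given for 40 names three factors, and the printed quotas cover one. No change follows.

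- **Sex.** The list may already cover it. If it does not, the average loss is about 4% to 6% in the standard error of an age-adjusted contrast that is not an aim. Turning away some 8 to 13 patients to recover that is a poor trade.
- **Hip pathology.** The split is unset, and adjustment is discretionary. Listing two procedure types and foreseeing adjustment for pathology suggests a factor that can vary, so the reading under which it is constant is the less natural one.
- **Age.** Unequal quotas are a choice of age mix. The overlap touches only patients aged exactly 50 and is a wording slip that the coordinator can settle. Age 70 is not ambiguous, because the top band starts above it. Age adjustment is already foreseen.

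The size of the loss rests on an assumed share of women between 50% and 60% and on sex falling by chance within fixed 20/10/10 age bands. A much more lopsided sex mix would cost more precision in the sex contrast. Even then, the width of the interval around a given pooled correlation would still be set by the 40 patients.
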